#### 12.1.4 Subject instructions

During the trial, the Subject will be allowed to use, if needed, all types of therapies excluding those listed in the exclusion criteria (section 9.2.2).

If a Subject need to take a concomitant treatment (topical or systemic), he/she should inform the Investigator of it as quickly as possible (at the latest, at the next visit).

The Subject will be instructed to keep the treated areas as dry as possible. Showers and baths are not allowed after the applications. In addition, the Subject will be instructed to avoid excessive sun exposure during the trial. During the trial, the Subject should avoid practicing strenuous exercises during the entire trial period.

Participation in any other clinical trial is prohibited during the course of the trial and for the following month.

## **13** Statistical Analysis

## 13.1 Trial population

All subjects recruited for the trial (i.e. signed informed consent obtained and a CRF Book started) will be accounted for in the trial report.

Clinical Trial Protocol MC2-01-C4

Final Approved Version 20/08/2018

All randomized subjects who receive any trial medication and who contribute any efficacy data in the trial will comprise the full analysis set and will be analyzed for efficacy.

A per protocol analysis set will be defined by exclusion of subjects from the full analysis set, who do not fulfil all of the inclusion criteria or who meet any of the exclusion criteria.

Further subjects and/or subject data may be excluded from the per protocol analysis when agreed upon on the basis of the actual data obtained as evaluated before breaking the randomization code.

All subjects who receive any treatment with trial medication and for whom the presence or confirmed absence of adverse events is available will be included in the safety analysis set and analyzed for safety.

The decisions regarding inclusion/exclusion of subjects and/or subject data from the trial analysis sets will be documented in the Statistical Analysis Plan Update before breaking the randomization code.

#### 13.1.1 Baseline characteristics

Descriptive statistics of demographics and other baseline characteristics will be presented for all randomized subjects.

Summary statistics of demographics (age and sex) and of baseline characteristics (height, weight, skin type, heart rate, systolic and diastolic blood pressure, concurrent diagnoses and concomitant medication at baseline) will be tabulated for all randomized subjects.

## 13.2 Analysis of pharmacodynamic effect (blanching)

The statistical analysis of efficacy will be based on the defined response criteria.

#### 13.2.1 Primary pharmacodynamic criterion

The analysed variable will be the mean between the two readers at each evaluation time.

The results will be expressed by the mean values obtained at each assessment time by product/site.

MC2-01 cream will be compared with Clobex lotion, Betamethasone Dipropionate (Augmented) cream, Triamcinolone Acetonide cream, Locoid® cream, DesOwen cream and MC2-01 cream vehicle in terms of visual score of skin blanching 2 hours after a 16 hours application, using an ANOVA with subjects and treatments as factors. The mean of visual assessments obtained at the same time points from 2 independent trained readers will be used. In case of a significant treatment effect, estimates of treatment effect and 95% confidence interval of differences between reference products and MC2-01 cream will be calculated from the model without correction for multiplicity in the primary analysis. Correction for multiplicity using Dunnett's test will be used as secondary analysis. In case of significant deviation to the normal assumption, a non-parametric approach with Kruskall-Wallis test for the overall product effect and Wilcoxon's Sign Rank Test for the pairwise comparisons will be used.

#### 13.2.2 Secondary pharmacodynamic criterion

#### Not Applicable

Page 45/54 This document will be regarded as confidential and proprietary in nature and will not be disclosed to any third party without sponsors written consent

Clinical Trial Protocol MC2-01-C4

### 13.3 Analysis of Safety

#### 13.3.1 Local safety

The local tolerance score will be summarized using frequency and percentage by visit and trial product. The worst score will also be summarized.

#### 13.3.2 Adverse events

Adverse events will be coded during the course of the trial and will be in accordance with the current version of the MedDRA dictionary. The adverse events will be tabulated by Preferred Terms and System Organ Class.

The number of subjects experiencing each type of adverse event (according to MedDRA Preferred Terms and System Organ Class) will be tabulated regardless of the number of times each adverse event is reported by each subject.

Adverse events where the investigator has not excluded a causal relationship to trial medication (i.e. not described relationship as "no reasonable possibility", adverse drug reactions) will be evaluated separately. A table or a description of these ADRs will be produced depending on the number of ADRs. As with adverse events, the number of subjects affected, not the number of events, will be considered.

The causal relationship of adverse events to trial medication and the intensity of adverse drug reactions will be tabulated or described. Where there are several recordings of causal relationship and intensity for the same event, causal relationship will be taken from the last report of the event (since that is when the investigator will be in possession of most information and so best able to judge causal relationship) and intensity will be taken as the worst ever recording. Adverse events observed on the application areas will be tabulated or described by treatment.

#### **13.4** General principles

All significance tests will be two-sided and all confidence intervals will be presented with 95% degree of confidence.

Categorical data will be summarized using the number and percentage of subjects in each category. Continuous data will be summarized using the mean, median, SD, minimum and maximum values.

Very few missing values from primary response criterion are expected. Usually less than 10% of randomized subjects do not attend the last visit in this kind of studies. Drop-outs and missing values will be accounted for by the analysis of end of treatment values using a last observation carried forward approach and by the definition of the trial analysis sets prior to unblinding. All the pre-specified analyses will be reviewed in relation to the blinded data actually obtained and the Statistical Analysis Plan Update will be finalized before breaking the randomization code.

Clinical Trial Protocol MC2-01-C4

### 13.5 Number of subjects calculation

The null hypothesis for each pairwise comparison will be no difference in the human skin blanching test :

H0: ∆ = 0,

where  $\Delta$  is the mean difference in visual score between test sites with the compared treatments. The standard assumptions of normality and independence will be used.

According to previous vasoconstriction trial performed by CPCAD, a maximal standard deviation for the difference of 0.65 is assumed.

Using a paired t-test, a two-sided significance level of 5%, with 30 complete subjects, the probability of detecting a difference of 0.5 units assuming a standard deviation for the difference of 0.65 is 98%.

MC2-01 cream will be compared to the five steroid-containing reference products giving at least 92% (0.98) power to obtain 5 significant differences if the true difference with each reference product is at least 0.5 int. MC2-01 cream will also be compared to the matching MC2-01 cream vehicle, but that will have negligible impact on the overall power assuming a difference of at least 1 point between both products.

A total of 36 subjects will be randomized in this trial in order to obtain at least 30 completed evaluable subjects.

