#### Short Title :

A vasoconstriction test trial with a MC2-01 cream (ranking trial).

Sponsor Trial Number:	MC2-01-C4
Clinical Trial Phase:	Phase 1
Investigator:	[name] [name]
Co-Investigator:	[name] [name]
Clinical Trial Population:	Healthy subjects, males and females, aged 18 to 50 years old.
Clinical Trial Objectives:	The objective of this trial is to compare the vasoconstriction potential (skin blanching effect) of MC2-01 cream with Clobex 0.05% (clobetasol propionate) lotion, Betamethasone Dipropionate (Augmented) 0.05% (betamethasone dipropionate) cream, Triamcinolone Acetonide 0.1% (triamcinolone acetonide) cream, Locoid ® 0.1% (hydrocortisone butyrate) cream, Desowen ® 0.05% (desonide) cream and MC2-01 vehicle using the human skin blanching test (McKenzie-Stoughton's test).
Background:	Topically applied corticosteroids elicit a pharmacologic activity (blanching) viewed by many as being "vasoconstrictive" in nature. The skin blanching effect was first described by Mc Kenzie and Stoughton (1) in 1962. This pharmacodynamic response has been correlated with the clinical efficacy of the product in psoriasis (2) and used for years to determine the clinical potency of topical corticosteroid formulations and to classify them within the US topical steroid potency classification.
	MC2 Therapeutics has developed an innovative dermal pharmaceutical formulation containing calcipotriol (CAL) 0.005 % w/w (50 $\mu$ g/g) and betamethasone dipropionate (BDP) 0.064 % w/w (0.5 mg/g as betamethasone), MC2-01 cream to ease local application of pharmaceuticals and to significantly enhance local cutaneous penetration of the active ingredients.
	Currently marketed products are restricted to non-oil-based formulations as calcipotriol and betamethasone are characterized by having a potential incompatibility to exist together in an environment, since calcipotriol requires basic conditions to maintain stability while betamethasone requires acidic conditions.

CPCAD Nice	C P C A D
Clinical Trial Protocol MC2-01-C4	Final Approved Version 20/08/2018
	MC2-01 cream has been formulated using the PAD ™ Technology allowing sufficient protection of the drug substances from degradation during storage.
Clinical Hypothesis:	The blanching effect of the MC2-01 cream is expected to be lower than Clobex, not significantly different from Betamethasone Dipropionate (Augmented) cream and higher than the other references.

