# 5.2.2 Rational for the reference products

In the US potency ranking of commonly used corticosteroids, Group I is the super-potent category. Potency descends with each group to group VII, which is the least potent.

In a ranking assay, the active reference products must be selected to ensure an adequate bracketing to determine the topical corticosteroid potency class of the MC2-01 cream (CA/BDP). It should also demonstrate that the IMP is not different from the target class representative.

The active reference products are listed below including their steroid potency description and Group and Class according to the 7-point US classification system. Several US classification charts (13) (14) (15) (16) and the WHO classification (17) have been used for reference and selection.

Generic name	Group /Class	Potency	Brand name	Rational
Clobetasol propionate 0.05%	I	Ultra High/Super potent	Clobex ® lotion	Highest potent
Betamethasone dipropionate 0.05 %	II	High/Potent	Betamethasone Dipropionate (Augmented) cream	Representative of the target potency group and matching steroid for the IMP
Triamcinolone acetonide 0.1%	IV	Medium	Triamcinolone Acetonide cream	Representative of a medium group
Hydrocortisone-17- butyrate 0.1%	V	Medium	Locoid ® cream	Representative of a lower medium group
Desonide 0.05%	VI	Low	Desowen ® cream	Lowest potency used in psoriasis (face or folds)

Page 17/54

This document will be regarded as confidential and proprietary in nature and will not be disclosed to any third party without sponsors written consent

Clinical Trial Protocol MC2-01-C4

Final Approved Version 20/08/2018

Group: From Stoughton (13), the American Academy of Family Physicians (16) and World Health Organization Classification of Topical Corticosteroids (17).

Class: Potency of Topical Corticosteroids (USA classification) (14).

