## 5.2 . Analysis of pharmacodynamic effect (blanching)

#### 5.2.1 Primary pharmacodynamic criterion

The analysed variable will be the mean between the two readers at each evaluation time.

The results will be expressed by the mean values obtained at each assessment time by product/site.

MC2-01 cream will be compared with Clobex® lotion, Betamethasone Dipropionate (Augmented) cream, Triamcinolone Acetonide cream, Locoid® cream, DesOwen® cream and MC2-01 cream vehicle in terms of visual score of skin blanching 2 hours after a 16 hours application, using an ANOVA with subjects and treatments as factors.

Some minor changes in the protocol statistical methods have been decided and reported in the SAP to improve the data analysis of the primary criterion.

The protocol planned that In case of a significant treatment effect, estimates of treatment effect and 95% confidence interval of differences between reference products and MC2-01 cream will be calculated from the model without correction for multiplicity in the primary analysis and that correction for multiplicity using Dunnett's test will be used as secondary analysis. In case of significant deviation to the normal assumption, a non-parametric approach with Kruskall-Wallis test for the overall product effect and Wilcoxon's Sign Rank Test for the pairwise comparisons will be used

The present Statistical Analysis Plan states that In case of a significant treatment effect, the comparisons between reference products and MC2-01 cream will be done from the model with correction for multiplicity using Dunnett's test directly in the primary analysis. For each fitted model, residual plots will be used to check the model assumptions. If there is an obvious deviation to these assumptions, the analysis will be done on the rank-transformed data.

The data will be also presented graphically by treatment using boxplot of visual assessment of skin blanching.

Statistical Analysis Plan MC2-01-C4 / CPCAD CPC-3530 Version 2.0 dated 05-Dec-2018 Page 14/16

The results will be presented as follows:

	MC2-01 cream (n=XX)	Clobex® lotion (n=XX)	Betamethasone Dipropionate (Augmented) cream (n=XX)	Triamcinolone Acetonide cream (n=XX)	Locoid® cream (n=XX)	Desowen® cream (n=XX)	MC2-01 cream vehicle (n=XX)
N Mean±SD Median (Min,Max)							
p-value a (treatment comparison versus MC2-01 cream)	-						

a: method used for multiple comparisons

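### The 92% power in Protocol 13.5 belongs to the uncorrected test; under the SAP's Dunnett-corrected primary analysis it is about 79–82% at 30 completers, and the five differences it counts include one the trial expects not to find

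*Protocol*

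**What the plan says.** Protocol 13.5 sets the basis of the calculation: "Using a paired t-test, a two-sided significance level of 5%, with 30 complete subjects", a difference of 0.5 units, and "a maximal standard deviation for the difference of 0.65 is assumed". It gives 98% power for one comparison and then describes the trial as "giving at least 92% (0.98) power to obtain 5 significant differences if the true difference with each reference product is at least 0.5". This matches Protocol 13.2.1, where the primary comparisons are uncorrected and Dunnett's test is secondary.

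SAP 5.2.1 reverses that order. The comparisons are to be "done from the model with correction for multiplicity using Dunnett's test directly in the primary analysis". The SAP sets out the old and new rules together and presents the change as minor. It contains no power or sample-size statement.

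On the expected result, the Clinical Hypothesis in the protocol synopsis says MC2-01 cream should blanch less than Clobex, be "not significantly different from Betamethasone Dipropionate (Augmented) cream and higher than the other references". Protocol 5.2.2 says of the ranking assay: "It should also demonstrate that the IMP is not different from the target class representative".

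**The concern.** The only power figure in the two documents describes a test that is no longer primary. Dunnett's test uses a larger critical value, so the probability of obtaining a full set of significant differences must be lower than stated.

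The event whose power is quoted is also not the event the trial expects. Five significant differences would include one from augmented betamethasone dipropionate, the representative of the target class, which MC2-01 is expected to match.

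This matters because the trial places MC2-01 in a potency class by bracketing, so the conclusion is the pattern of separations. A reader relying on 13.5 would think a missed separation has at most about an 8% chance when the true differences are 0.5, and could read a single non-significant comparison as stronger evidence of similarity than it is.

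**Working it through.** **Inputs.** Difference 0.5, SD of the paired difference 0.65, 30 completers and 36 randomized (Protocol 13.5). ANOVA with subject and treatment factors, seven treatments, six comparisons with MC2-01 (SAP 5.2.1). Two-sided 0.05 (SAP 5.4). Subjects with a missing primary score are excluded (SAP 5.4.1), so the analysis runs on completers.

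**Reproducing 13.5.**
- Noncentrality = 0.5 / (0.65/√30) = 0.5 / 0.1187 = 4.213.
- Paired t-test, 29 df, critical value 2.045: power 0.9826 (stated 98%).
- All five, treated as independent: 0.9826^5 = 0.916 (stated 92%). Allowing for the shared MC2-01 site gives 92.5–93.3%.

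The stated figure is therefore sound for its own test.

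**Moving to the ANOVA, still uncorrected.** With pooled variance and 6 × 29 = 174 error df, the critical value is 1.97. Power is 98.7% per comparison, 94.5–95.0% for all five and 95.4% for the four references other than betamethasone dipropionate. These are the like-for-like starting points for what follows.

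**Applying Dunnett.** Write T_i = [(Z_i − Z_0)/√2 + g_i × noncentrality] / S. Z_0 is the shared MC2-01 term, g_i = ±1 is the direction of the difference, and S² is chi-square on 6(n−1) df divided by its df. The statistics have correlation 0.5. The critical value c solves P(max |T_i| ≤ c) = 0.95 over six comparisons: 2.59 at n = 30, 33 and 36.

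| Completers | One comparison | All five references | Four references, without betamethasone dipropionate |
|---|---|---|---|
| 30 | 94.6% | 79.4–82.5% | 82.1% |
| 33 | 96.5% | 86.2–87.9% | 88.1% |
| 36 | 97.8% | 90.9–91.9% | 92.3% |

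In the all-five column, the lower value has Clobex on the opposite side from the rest and the upper value has all five on one side. The last column puts Clobex above MC2-01 and the other three below, as the hypothesis expects.

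**Chance of missing at least one of the four.** 100 − 82.1 = 17.9% at 30, 100 − 88.1 = 11.9% at 33, and 100 − 92.3 = 7.7% at 36.

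**Sensitivity.**
- Vehicle left out of the Dunnett family (five comparisons, critical value 2.54): all-five power at 30 is 81.5–84.1%.
- SD 0.60 instead of 0.65 (an assumption): four-reference power is 91% at 30 and 95% at 33.
- Likely completers: Protocol 13.4 says "Usually less than 10% of randomized subjects do not attend the last visit in this kind of studies". Since 0.9 × 36 = 32.4, that means at least 33.

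**The count of five.** If betamethasone dipropionate truly does not differ and the other four differ by 0.5, five significant differences occur about 4% of the time uncorrected and about 0.5% under Dunnett (n = 30). The quoted event is then almost unattainable, although the trial would be going as expected.

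**The case against.** The strongest reply is that 13.5 is not wrong. It describes the protocol's own test, reproduces there, and is conditional on a difference of at least 0.5 with each reference. Dunnett was already in the protocol as a secondary analysis, and the SAP discloses the change openly. All of that stands: the gap is the SAP's failure to restate power, not an arithmetic error in the protocol.

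Second, 79–82% is the pessimistic corner: the minimum number of completers, an SD described as maximal, and every difference at the 0.5 floor. Protocol 5.2.2 places triamcinolone, Locoid and Desowen in classes IV, V and VI, so their differences from MC2-01 may well widen. With illustrative differences of 0.5 (Clobex), 0.5, 0.6 and 0.7 (an assumption), four-reference power under Dunnett is 89% at 30, 93% at 33 and 95% at 36. This also stands. For the planned SD and 30 completers, 18% is the upper end of the miss rate under 13.5's condition. But these are the values on which 13.5 itself quotes power, so they are the right ones for comparison.

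Third, power for all five is a lower bound for any four, so 92% still holds for the expected pattern under the uncorrected test. That is correct, but it does not carry over to Dunnett at 30 completers. Power to detect 0.5 against betamethasone dipropionate is also informative, because it shows what a non-significant result could have missed. The per-comparison figure should therefore stay visible.

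Finally, SAP 5.2.1 allows a switch to rank-transformed data, to which none of these figures apply. Any restatement should say so.

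**Conclusion.** The concern holds. The stated 92% describes neither the current primary analysis nor the expected pattern of results. At 30 completers, power under Dunnett is 94.6% per comparison, 79–82% for all five references and 82% for the four expected to separate. The last figure rises to 88% at 33 completers and returns to 92% only if all 36 are evaluable.

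These figures assume a true difference of exactly 0.5, an SD of difference of 0.65 that is equal across pairs, pooled ANOVA variance, correlation 0.5 and a Dunnett family of six. A smaller SD, larger differences or a family of five would raise them. The consequence is limited to how a non-significant comparison is read; estimates and p-values are unaffected.

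**What to change.** Keep Dunnett's test as the primary analysis. Add to the SAP and the study report a statement such as:

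> The 92% power in protocol section 13.5 applies to the uncorrected paired t-test. For the Dunnett-corrected ANOVA (six comparisons, pooled variance, SD of difference 0.65, true difference 0.5), power is about 95% per comparison at 30 completers. Power to separate MC2-01 cream from all four of Clobex, triamcinolone acetonide, Locoid and Desowen is about 82% at 30 completers, 88% at 33 and 92% at 36. These figures do not apply to the rank-transformed analysis.

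Take betamethasone dipropionate out of the count of significant differences. The per-comparison figure still covers it as power to detect 0.5. Quote no power for showing similarity, because the documents give no margin.

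The cost is a few sentences and a less favourable headline figure. No subjects are added: SAP version 2.0 is dated 05-Dec-2018, after the last subject out planned for October 2018, so this is a reporting correction.

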## 14 TRAINING / MONITORING / DATA MANAGEMENT / QUALITY ASSURANCE

## 14.1 Personnel training

A trial initiation visit will be conducted by the Sponsor with the Investigator and the trial team. During this meeting, an extensive review and discussion of the protocol, procedures, CRF and any other trial material will be conducted. Sponsor's monitoring visits will be performed.

Clinical Research Associates (CRAs) and other applicable personnel will be trained prior to trial initiation to familiarize CRAs with the disease, the Standard Operating Procedures (SOP), the protocol and other trial specific items. Team organization, communication and operational issues will also be discussed.

## 14.2 Clinical monitoring

The conduct of the clinical trial will be closely monitored by the sponsor's designee (Adhoc Clinical, [name]) to verify adherence to the clinical trial protocol, ICH GCP guidelines, and applicable SOPs.

The Investigator will allow the CRO/Sponsor's representatives, to have direct access to all clinical trial records, CRFs, corresponding subject medical records, trial drug(s) dispensing records, trial drug(s) storage area, clinical trial facilities, and any other documents considered source documentation.

Clinical Trial Protocol MC2-01-C4

The Investigator also agrees to assist the representative if required.

